8.3.4. Treatment of adverse events

Any medication administered for the treatment of an SAE should be recorded in the Expedited Adverse Event Report of the participant's eCRF screen (refer to the Section 10.3.8.1).

8.3.5. Participant card

The investigator (or designee) must provide the participant's parent(s)/LAR(s) with a "participant card" containing information about the clinical study. The participant's parent(s)/LAR(s) must be instructed to keep the participant card in his/her/their possession at all times throughout the study. In an emergency, this card serves to inform the responsible attending physician/LAR/care giver/family member that the participant is in a clinical study and that relevant information may be obtained by contacting the investigator.

8.3.6. Medical device deficiencies

Both study groups have study interventions that are a combination product constituted of a device (e.g., **CCI** [REDACTED]) and biologic product. Refer to the **Glossary of terms** for the definition of combination product and medical device deficiency.

8.3.6.1. Detection, follow-up, and prompt reporting of medical device deficiency

The investigator is responsible for the detection, documentation and prompt reporting of any medical device deficiency occurring during the study to GSK. This applies to any medical device provided for the conduct of the study.

Device deficiencies will be reported to GSK within 24 hours after the investigator determines that the event meets the protocol definition of a device deficiency. Refer to Section 10.4 for definitions and details on recording and reporting of these events.

The investigator will ensure that follow-up includes any additional investigations to elucidate the nature and/or relatedness of the device deficiency to the incident.

New or updated information will be recorded on the originally completed form with all changes signed and dated by the investigator and reported to GSK within 24 hours.

Medical device deficiencies and any associated AE/SAEs for associated person (i.e., spouse, caregiver, site staff) will also be collected. The associated person will be provided with a safety reporting information and authorization letter.

Follow-up applies to all participants, including those who discontinue study intervention or the study, and associated persons.

8.3.6.2. Regulatory reporting of medical device deficiency when used as combination product

The investigator will promptly report all device deficiencies occurring with any medical device provided for use in the study to GSK. GSK has a legal responsibility to notify appropriate regulatory authorities and other entities about safety information linked to medical devices being used in clinical studies. Refer to Section 10.4.3 for details of reporting.

The investigator, or responsible person according to local requirements (e.g., the head of the medical institution), will comply with the applicable local regulatory requirements linked to the reporting of device deficiencies to the IRB/IEC.

8.4. Treatment of overdose

This section is not applicable.

8.5. Pharmacokinetics

Pharmacokinetic parameters are not evaluated in this study.

8.6. Pharmacodynamics

Pharmacodynamic parameters are not evaluated in this study.

8.7. Genetics

This section is not applicable.

8.8. Biomarkers

This section is not applicable.

8.9. Health outcomes

This section is not applicable.

9. STATISTICAL CONSIDERATIONS

9.1. Statistical hypotheses

This section is not applicable

9.2. Sample size determination

A maximum of 2000 participants (1000 per arm) will be randomized such that approximately 1500 evaluable participants complete the study, considering that 25% of the participants will not be evaluable for the analysis of the primary endpoint leading to 750 evaluable participants per arm.

To control the type 1 error for the primary objectives and first secondary objective a hierarchical procedure will be used. Namely the primary objective on ratio of anti-RV IgA Ab GMCs will be conclusive if the success criterion is reached and the first primary objective is met. The first secondary objective will be conclusive if the success criterion is reached and the 2 primary objectives are met.

The sample size provides at least 90% power to reach the first primary endpoint (see [Table 13](#)) and at least 80.7% power to reach the second primary endpoint. 80.7% is a very conservative power estimate and is obtained as 100% minus the sum of type II errors for the 2 primary objectives, see [Table 13](#) and [Table 14](#). Using the same approach, the power to meet the first secondary objectives will be at least 67% power.

9.2.1. Power for non-inferiority in seroconversion

The power presented in [Table 13](#) is based on PASS 2019 (one-sided Non-Inferiority Tests for the Difference Between Two Proportions), under the alternative of a 70% and 67.8% seroconversion rate for *Rotarix* and *Rotarix* PCV-free, respectively, Miettinen and Nurminen's Likelihood Score Test of the Difference).

Table 13 Probability that the lower limit of the 95% CI around group difference in seroconversion rate (*Rotarix* PCV-free minus *Rotarix*), 1 month after Dose 2 of *Rotarix*, is greater or equal to -10%

Expected Seroconversion rate (Rotarix / Rotarix PCV-free)	N evaluable (each Rotarix group)	Power	Alpha
70%* / 67.8%	750	90%	0.025

* = Reference from [Rota-075](#)

9.2.2. Power for non-inferiority in GMC

The power presented in [Table 14](#) is based on PASS 2019 (one-sided non-inferiority test for 2 independent means, under the alternative of equal variance & alpha=2.5%).

Table 14 Probability that the lower limit of the 95% CI around the anti-RV IgA Ab GMC ratio (*Rotarix* PCV-free / *Rotarix*), 1 month after Dose 2 of *Rotarix*, is greater or equal to 0.67

Endpoint	True group GMC ratio	Standard deviation [Log_{10} (titer)]	N evaluable (each Rotarix group)	Power	Alpha
Anti-RV IgA Ab concentration	1	0.797*	750	99.0%	0.025
Anti-RV IgA Ab concentration	0.91	0.797*	750	90.7%	0.025

* = Reference from [Rota-075](#)

9.2.3. Power for non-inferiority in the percentage of participants with serum anti-RV IgA antibody concentrations greater or equal to 90 U/mL 1 month post Dose 2

The power presented in [Table 15](#) is based on PASS 2019 (one-sided Non-Inferiority Tests for the Difference Between Two Proportions), under the alternative of a 45.7% and 43.5% percentage for *Rotarix* and *Rotarix* PCV-free, respectively, Miettinen and Nurminen's Likelihood Score Test of the Difference).

Table 15 Probability that the lower limit of the 95% CI around group difference in the percentage of participants with serum anti-RV IgA antibody concentrations greater or equal to 90 U/mL (*Rotarix* PCV-free minus *Rotarix*), 1 month after Dose 2 of *Rotarix*, is greater or equal to -10%

Expected rate (Rotarix / Rotarix PCV-free)	N evaluable (each Rotarix group)	Power	Alpha
45.7%* / 43.5%	750	86.2%	0.025

* = Reference from [Rota-075](#)

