3. OBJECTIVES AND ENDPOINTS

Table 3 Study objectives and endpoints

[figure not shown]
Objectives	Endpoints
	
Primary
 
 • To demonstrate the immunological non-inferiority of Rotarix PCV-free as compared to Rotarix in terms of seroconversion rates 1 month post Dose 2. 
 - Non-inferiority will be demonstrated if the lower limit of the two-sided asymptotic standardized 95% CI for the difference in seroconversion rate between the Rotarix PCV-free and Rotarix is greater than or equal to -10%. • To demonstrate the non-inferiority of the Rotarix PCV-free as compared to Rotarix in terms of serum anti-RV IgA Ab concentrations 1 month post Dose 2. 
 - Non-inferiority will be demonstrated if the lower limit of the two-sided 95% CI for the ratio of anti-RV IgA Ab geometric mean concentration (GMC) 1 month post Dose 2 between the Rotarix PCV-free and Rotarix is greater than or equal to 0.67.
	
Secondary
 
 • To assess the immunological non-inferiority of Rotarix PCV-free as compared to Rotarix in terms of percentage of participants with anti-RV IgA antibody concentrations ≥ 90 U/mL 1 month post Dose 2. 
 - Non-inferiority will be demonstrated if the lower limit of the two-sided asymptotic standardized 95% CI for the difference in the percentage between the Rotarix PCV-free and Rotarix is greater than or equal to -10%. • To evaluate the reactogenicity of Rotarix PCV-free and Rotarix in terms of solicited systemic events. • To assess the safety of Rotarix PCV-free and Rotarix in terms of unsolicited AEs and serious adverse events (SAEs).

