# 5. SAMPLE SIZE DETERMINATION

A maximum of 2000 participants (1000 per arm) will be randomized such that approximately 1500 evaluable participants complete the study, considering that 25% of the participants will not be evaluable for the analysis of the primary endpoint leading to 750 evaluable participants per arm.

To control the type 1 error for the primary objectives and first secondary objective a hierarchical procedure will be used. Namely the primary objective on ratio of anti-RV IgA Ab GMCs will be conclusive if the success criterion is reached and the first primary objective is met. The first secondary objective will be conclusive if the success criterion is reached and the 2 primary objectives are met.

The sample size provides at least 90% power to reach the first primary endpoint (see [Table 3](#)) and at 80.7% power to reach the second primary endpoint. 80.7% is a very conservative power estimate and is obtained as 100% minus the sum of type II errors for the 2 primary objectives, see [Table 3](#) and [Table 4](#). Using the same approach, the power to meet the first secondary objectives will be at least 67% power.

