### 5.1.2. Power for non-inferiority in GMC

The power presented in [Table 4](#) is based on PASS 2019 (one-sided non-inferiority test for 2 independent means, under the alternative of equal variance & alpha=2.5%).

**Table 4 Probability that the lower limit of the 95% CI around the anti-RV IgA Ab GMC ratio (*Rotarix* PCV-free / *Rotarix*), 1 month after Dose 2 of *Rotarix*, is  $\geq 0.67$**

Endpoint	True group GMC ratio	Standard deviation [ $\text{Log}_{10}$ (titer)]	N evaluable (each Rotarix group)	Power	Alpha
Anti-RV IgA Ab concentration	1	0.797*	750	99.0%	0.025
Anti-RV IgA Ab concentration	0.91	0.797*	750	90.7%	0.025

\* = Reference from Rota-075

N = number of participants

### 5.1.3. Power for non-inferiority in the percentage of participants with serum anti-RV IgA antibody concentrations greater or equal to 90 U/mL 1 month post Dose 2

The power presented in [Table 5](#) is based on PASS 2019 (one-sided Non-Inferiority Tests for the Difference Between Two Proportions), under the alternative hypothesis of a 45.7% and 43.5% percentage for *Rotarix* and *Rotarix* PCV-free, respectively, [Miettinen](#) and [Nurminen](#)'s Likelihood Score Test of the Difference).

**Table 5 Probability that the lower limit of the 95% CI around group difference in the percentage of participants with serum anti-RV IgA antibody concentrations greater or equal to 90 U/mL (*Rotarix* PCV-free minus *Rotarix*), 1 month after Dose 2 of *Rotarix*, is  $\geq -10\%$**

Expected rate ( Rotarix / Rotarix PCV-free)	N evaluable (each Rotarix group)	Power	Alpha
45.7%* / 43.5%	750	86.2%	0.025

\* = Reference from Rota-075

N = number of participants

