### 6.2.10. Number of decimals displayed

The following decimal description from the decision rules will be used for the demography, immunogenicity and safety/reactogenicity.

Display Table	Parameters	Number of decimal digits
All summaries	% of count, including LL & UL of CI	1
Demographic characteristics	Mean, median, SD	1
Reactogenicity	% of count, including LL & UL of CI	1
Immunogenicity	GMCs and Rates (%), including LL & UL of CI	1
Immunogenicity	GMC ratios, including LL & UL of CI	2
Immunogenicity	Differences between Rates, including LL & UL of CI	2

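### Minor: the printed GMC power (99.0% and 90.7%) does not follow from the stated 0.67 limit, which gives 98.8% and 89.8%; a limit of 2/3 would reproduce both printed figures

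*Protocol*

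**What the plan says.** The second primary objective succeeds if the lower limit of the two-sided 95% CI for the GMC ratio (PCV-free over *Rotarix*) "is greater than or equal to 0.67" (Protocol 3, Table 3). SAP 1.1 and SAP 2 give the same limit, and neither document mentions 2/3.

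Protocol 9.2.2 and SAP 5.1.2 describe the power calculation as a "one-sided non-inferiority test for 2 independent means, under the alternative of equal variance & alpha=2.5"%. Protocol Table 14 and SAP Table 4 use an SD of 0.797 log10 and 750 evaluable per arm, and print 99.0% at a true ratio of 1 and 90.7% at 0.91. The title of Protocol Table 14 defines this power as the probability that the lower limit "is greater or equal to 0.67", and the title of SAP Table 4 states the same limit.

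Protocol 9.2 carries the 90.7% forward. It claims "at least 80.7% power to reach the second primary endpoint", and SAP 5 explains that "80.7% is a very conservative power estimate and is obtained as 100% minus the sum of type II errors" for the two primary objectives. Protocol 9.2 then adds: "Using the same approach, the power to meet the first secondary objectives will be at least 67% power".

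**The concern.** A power figure printed to one decimal should be recoverable from the inputs printed beside it. Neither GMC figure is, and both err on the favourable side. The row at a true ratio of 0.91 matters more, because it is the term added into the two lower bounds. At the stated criterion its power falls just below 90%, and neither bound follows from the plan's own rule.

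What is at stake is the accuracy of the stated power for the criterion that decides the second primary objective. It is also worth having on record which margin the calculation used, since the text knows only 0.67.

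**Working it through.** **Inputs** (Protocol Table 14 and SAP Table 4): SD 0.797 log10; n = 750 per arm; one-sided alpha 0.025; true ratio R = 1 or 0.91; limit M = 0.67. From Protocol Tables 13 and 15: power 90% for seroconversion and 86.2% for the ≥ 90 U/mL endpoint.

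**Formula.** Two-sample t-test on log10 concentrations with equal variances:

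- SE = 0.797 × √(2/750) = 0.04116; df = 1498; critical t = 1.9615
- noncentrality δ = (log10 R − log10 M) / SE
- power = P(noncentral t with parameter δ exceeds 1.9615)

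**At the stated limit, M = 0.67** (log10 = −0.17393; log10 0.91 = −0.04096):

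- R = 1: δ = 0.17393 / 0.04116 = 4.226, power 98.82%
- R = 0.91: δ = (0.17393 − 0.04096) / 0.04116 = 3.231, power 89.77%

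**At other limits:**

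| Limit M | R = 1 | R = 0.91 |
|---|---|---|
| 0.665 | 99.04% | 91.11% |
| 2/3 | 98.97% | 90.68% |
| 0.67 | 98.82% | 89.77% |
| 0.675 | 98.56% | 88.30% |
| Printed | 99.0% | 90.7% |

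The plan's figures are thus reproduced at 2/3 and not at 0.67. With the other inputs held at their printed values, a scan in steps of 0.00001 finds that only limits from 0.66640 to 0.66677 round to both printed powers.

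**Could another input explain the gap at 0.67?**

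- SD: 0.7965 to 0.7975 (all printing as 0.797) gives 98.8% at R = 1 and 89.7% to 89.8% at R = 0.91. No.
- True ratio: 0.905 to 0.915 (printing as 0.91) gives 88.7% to 90.8%. This could explain the second row but not the first, where R = 1.
- Alpha: one-sided 0.05 gives 99.5% and 94.3%. No.
- Sample size: 775 per arm gives 99.02% and 90.69%, which matches, but both documents say 750 throughout.

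**Effect on the bounds** (100% minus the sum of the type II errors):

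- As printed: 100 − 10 − 9.3 = 80.7%; 100 − 10 − 9.3 − 13.8 = 66.9%, printed as 67%.
- At 0.67 with the printed 90% and 86.2%: 90 + 89.8 − 100 = 79.8%; 90 + 89.8 + 86.2 − 200 = 66.0%.
- At 0.67 with Miettinen–Nurminen powers from full binomial enumeration (90.51% and 86.24%): 90.51 + 89.77 − 100 = 80.3%; 90.51 + 89.77 + 86.24 − 200 = 66.5%.

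**Joint power at 0.67 if the endpoints were independent:**

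- Printed component powers: 0.90 × 0.8977 = 80.8%; × 0.862 = 69.6%.
- Unrounded component powers: 0.9051 × 0.8977 = 81.3%; × 0.8624 = 70.1%.

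**The case against.** The strongest reply is that nothing the trial relies on is shown to be false. Under independence the joint power at 0.67 still exceeds both 80.7% and 67%. Positive correlation is plausible, since all three endpoints come from the same Visit 3 IgA result, and would raise it further. The plan itself calls the bound very conservative. This stands, and it is why the point is minor.

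Second, the gap is no larger than the rounding in the inputs. The 0.91 alone spans 88.7% to 90.8% at 0.67, which covers the printed 90.7%. That is true of this row, but no rounding of 0.91 can move the row at a true ratio of 1. If the ratio may be rounded as well as the margin, limits of about 0.6648 to 0.6671 fit both rows. That window is wider than the one above, but it still contains 2/3 and excludes 0.67.

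Third, the cause cannot be seen. The software output is not in the documents, and 775 per arm would fit equally well. SAP 6.2.10 sets two decimals for "GMC ratios, including LL & UL of CI", so 2/3 would display as 0.67, but that rule governs reported results and is weak evidence about planning inputs. This also stands: 2/3 is an inference. The shortfall at 0.67 does not depend on it.

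Fourth, the printed 90% for seroconversion is itself rounded down, which offsets part of the effect on the bounds. That is correct, and both bases are shown above.

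**Conclusion.** The concern holds as a minor arithmetic point. At the only limit the documents state, the printed inputs give 98.8% and 89.8%, so the tables overstate power by 0.2 and 0.9 points. The lower bound for the second primary moves from 80.7% to between 79.8% and 80.3%. That for the first secondary moves from 67% to between 66.0% and 66.5%. In each case the lower figure uses the printed component powers and the higher one uses unrounded powers.

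This rests on the printed SD, ratio and sample size being the values used, and on an equal-variance two-sample t-test as the documents describe. The recomputation is firm; the explanation by 2/3 is likely but unproven. Only the stated power and the lower-bound arithmetic change. The 0.67 criterion is consistent across both documents, and the sample size is not called into question.

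**What to change.** - In Protocol Table 14 and SAP Table 4, restate the power at 0.67 as 98.8% (true ratio 1) and 89.8% (true ratio 0.91).
- In Protocol 9.2 and SAP 5, restate the two bounds as about 80% and about 66%, still labelled conservative.
- Add a footnote to both tables giving the unrounded margin entered in the software. If another input differed from what is printed, say so there.
- Leave the 0.67 decision rule, the enrolment target and the analysis as they are.

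The cost is wording in four sections and a stated power up to about one point lower.

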9.3. Populations for analyses

Table 16 Populations for analyses

Analysis set	Description
Screened	All participants who were screened for eligibility
Enrolled Set	All participants who entered the study (who were randomized or received study intervention or underwent a post-screening study procedure). Note: screening failures (who never passed screening even if rescreened) and participants screened but never enrolled into the study (met eligibility but not needed) are excluded from the Enrolled Analysis set as they did not enter the study.
Exposed Set (ES)	All participants with at least 1 dose of the study intervention documented. The allocation in a group is done in function of the administered intervention. The ES analysis will be performed per treatment actually administered at Dose 1.
Per Protocol Set (PPS)	All eligible participants from the ES who meet all the following requirements: 
 • who received the study interventions according to their random assignment and the expected study intervention administration schedule (see Table 2). Note that in case regurgitation or vomiting occurs within 30 minutes after study intervention administration and impairs up-take of the intervention, a single replacement dose should be used for the participant to be part of the PPS, • who were not unblinded, • who did not receive a vaccine not specified or forbidden in the protocol up to Visit 3 blood sampling, • who did not receive medication forbidden by the protocol up to Visit 3 blood sampling, • who had anti-RV concentration below 20 U/mL before study intervention administration and who had anti-RV results from the Visit 3 blood sampling, • who complied with the blood sampling schedule for Visit 3 (see Table 2), • who had no concomitant infection up to Visit 3 blood sample, which may influence the immune system.

9.4. Statistical analyses

9.4.1. General considerations

9.4.1.1. Immunogenicity

Ab concentrations below the assay cut-off will be given an arbitrary value of half the assay cut-off for the purpose of GMC calculation.

- The GMC calculations will be performed by taking the anti-log of the mean of the log concentration transformations. Ab concentrations below the cut-off of the assay will be given an arbitrary value of half the cut-off for the purpose of GMC calculation.
- For a given participant and a given immunogenicity measurement time point, missing or non-evaluatable measurements will not be replaced.

9.4.1.2. Reactogenicity/Safety

Participants who missed reporting events (solicited/unsolicited AEs or concomitant medications) will be treated as participants without the events (solicited/unsolicited AEs or concomitant medications, respectively).

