9.4.4. Analysis of safety

Safety analysis will be performed on the ES.

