#### 4.1.2. Reactogenicity

Participants without events (solicited/unsolicited AEs or concomitant medications) reported will be treated as participants without the events (solicited/unsolicited AEs or concomitant medications, respectively).

Refer to Section 6.2.4.2 for the intensity grading of solicited AEs.

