#### 4.5. Safety Analyses

The analyses will be descriptive and conducted on the ES.

The following calculations will be performed for each group:

- The percentage of doses and participants reporting at least 1 AE (solicited or unsolicited) during the 14-day (Day 1 to Day 14) solicited follow-up period will be computed, along with exact 95% CI. The same calculations will be done for AEs (solicited or unsolicited) rated as grade 3 in intensity and for AEs leading to a medically attended visit.
- The percentage of doses over the study and the percentage of participants (by dose and over the study) reporting each individual solicited systemic event will be computed, over the 14-day (Day 1 to Day 14) solicited follow-up period, following study intervention administration, along with exact 95% CI. The same calculations will be done for each individual solicited systemic event rated as grade 3 (grade 3 or grade 4 for fever) in intensity and events leading to a medically attended visit. Temperature above specific thresholds will also be summarized with threshold defined by half degree increment.

*Note: Intensity of fever will be assessed by considering the grading scales recommended by the Chinese authorities [NMPA 2019b].*

- The verbatim reports of unsolicited AEs will be reviewed by a physician and will be coded according to MedDRA. Every verbatim term will be matched with the appropriate Preferred Term. The percentage of participants with unsolicited AEs occurring within 31-day (Day 1 to Day 31) follow-up period after any dose with its exact 95% CI will be tabulated by Preferred Term. The same calculations will be done for each AE rated as grade 3 in intensity, for AEs leading to a medically attended visit and for AEs causally related to HRV as per the investigator assessment.
- The percentage of participants reporting the occurrence of SAEs (any, related, fatal, fatal related) from Dose 1 of the study intervention up to study end with its exact 95% CI will be tabulated by study group and by preferred term.
- The percentage of participants reporting the occurrence of SAEs (any, related, fatal, fatal related) within 31-day (Day 1 to Day 31) follow-up period after any dose with its exact 95% CI will be tabulated by study group and by preferred term.
- SAEs and drop outs due to AEs will be described in detail.

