### 6.2.4.2. Daily recording of solicited AEs

When a specific solicited AE is marked as having not occurred following a specific vaccination (i.e. SDTM CE.CEOCCUR=N for the specified post-vaccination period for the solicited AE in question), all daily measurements will be imputed as Grade 0.

When a specific solicited AE is marked as having occurred following a specific vaccination (i.e. SDTM CE.CEOCCUR=Y for the specified post-vaccination period for the solicited AE in question), any missing daily recordings will be given an imputed value which allows them to contribute to the 'Any' rows but not to specific grade rows of the solicited AE summary tables.

When the occurrence of a specific solicited AE is not present (i.e. SDTM CE.CEOCCUR is neither Y nor N for the specified post-vaccination period for the solicited AE in question) all missing daily recordings will be given an imputed value which allows them to contribute to the 'Any' rows but not to specific grade rows of the solicited AE summary tables.

The following table shows how solicited events are coded for intensity.

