**Table 6      Intensity scales for solicited AEs – Attribution for codes for Diarrhea, Vomiting and Fever**

Event	Infant		
	Intensity grade (collected or measured)	Intensity grade (code attributed)	Parameter
Loss of appetite	0	0	Appetite as usual
	1	1	Eating less than usual/no effect on normal activity
	2	2	Eating less than usual/interferes with normal activity
	3	3	Not eating at all
Irritability/Fussiness	0	0	Behavior as usual
	1	1	Crying more than usual/no effect on normal activity
	2	2	Crying more than usual/interferes with normal activity
	3	3	Crying that cannot be comforted/prevents normal activity
Cough/runny nose	0	0	Normal
	1	1	Cough/runny nose which is easily tolerated
	2	2	Cough/runny nose which interferes with daily activity
	3	3	Cough/runny nose which prevents daily activity
Diarrhea	looser than normal stools/day	0	Normal (0-2 looser than normal stools/day)
		1	3 looser than normal stools/day
		2	4-5 looser than normal stools/day
		3	≥ 6 looser than normal stools/day
Vomiting	episodes of vomiting/day	0	Normal (no emesis)
		1	1 episode of vomiting/day
		2	2 episodes of vomiting/day
		3	≥3 episodes of vomiting/day
Fever †	Axillary Temperature (°C)	0	Normal (< 37.5°C)
		1	37.5°C – < 38.0°C
		2	38.0°C – < 39.5°C
		3	≥ 39.5°C
		4	≥ 39.5°C, lasts more than 5 consecutive days

†Axilla is the preferred route to measure temperature in China. If temperature is collected by other routes, the following conversion will be applied:

- Axillary temperature = oral temperature - 0.2°C;
- Axillary temperature = rectal temperature - 0.3°C.

The following table shows how participants contribute to each category for a specific solicited AE over the Day X to Day Y post-vaccination period:

Solicited AE category	Participants included in the calculation of the numerator
Any	All participants with at least 1 occurrence of the solicited AE at grade 1, grade 2, grade 3 or grade 4 between Day X and Day Y or with the solicited AE marked as present and at least 1 missing daily recording between Day X and Day Y
At least grade 1	All participants with at least 1 occurrence of the solicited AE at grade 1, grade 2, grade 3 or grade 4 between Day X and Day Y
At least grade 2	All participants with at least 1 occurrence of the solicited AE at grade 2, grade 3 or grade 4 between Day X and Day Y
At least grade 3	All participants with at least 1 occurrence of the solicited AE at grade 3 or grade 4 between Day X and Day Y

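### For solicited events, the plan treats an infant with no diary data in three incompatible ways and names no diary-based denominator

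*Protocol*

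**What the plan says.** Three statements govern an infant for whom nothing is recorded about a solicited event.

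- **General rule.** Protocol 9.4.1.2: "Participants who missed reporting events (solicited/unsolicited AEs or concomitant medications) will be treated as participants without the events". SAP 4.1.2 has nearly the same rule: "Participants without events (solicited/unsolicited AEs or concomitant medications) reported will be treated as participants without the events". Both name solicited events explicitly.
- **Derivation rule.** SAP 6.2.4.2 deals with the case where "SDTM CE.CEOCCUR is neither Y nor N" and says that "all missing daily recordings will be given an imputed value which allows them to contribute to the 'Any' rows". The same sentence keeps those values out of the grade-specific rows.
- **Contribution table.** The unnumbered table after Table 6, also in SAP 6.2.4.2, defines the Any numerator. Besides infants with a graded occurrence, it admits only those "with the solicited AE marked as present and at least 1 missing daily recording between Day X and Day Y".

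On the analysis set, Protocol 9.4.4 says "Safety analysis will be performed on the ES" and SAP 4.5 says "The analyses will be descriptive and conducted on the ES". Protocol 9.3 defines that set as "All participants with at least 1 dose of the study intervention documented", so a returned diary is not a condition of entry. The contribution table defines numerators only, and no section gives a denominator based on diary data. SAP 4.8 declares no change from the protocol's analyses.

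**The concern.** Solicited events are captured on a paper diary (Protocol 10.3.6). For unsolicited events, silence after open questioning at a visit is fair evidence that nothing happened. An unreturned diary is simply missing data. The plan does not replace missing immunogenicity values, yet for solicited events it assigns a value to missing diary data, and which value depends on the section followed.

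Reactogenicity is a stated secondary objective. Two programmers working from the same SAP could produce different Any rows from the same data, one below the true rate and one above it. If diary return differs between groups, the rule chosen also decides which group looks better tolerated.

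**Working it through.** **Inputs.** The plan states no diary return rate and no expected solicited-event rate, so it has no figure of its own to reproduce. Assumed ranges: true per-dose event rate p from 1% to 50%, and non-return m from 1% to 10%. Two further assumptions are that return is unrelated to the event, and that an unreturned diary leaves the occurrence flag as neither Y nor N. The base is the Exposed Set, as SAP 4.5 implies. The plan randomizes up to 1000 infants per arm.

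**Step 1: what each rule does to a non-returner.**

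- General rule: event-free, so outside every numerator. The Any row is p(1−m).
- Derivation rule: inside the Any numerator. The Any row is p(1−m) + m.
- Contribution table: outside the Any numerator, because the event is not marked as present. On this base the Any row is again p(1−m).

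The three wordings therefore give two numerical answers. The gap between them is exactly m percentage points, whatever p is.

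**Step 2: grade-specific rows.** No rule puts a non-returner into a grade row. A true grade 3 rate g is reported as g(1−m) under all three. With m = 5% that is a relative loss of 5%.

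**Step 3: Any rows, by dose.**

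| Assumed p | Assumed m | Non-returner not counted: p(1−m) | Non-returner in Any: p(1−m)+m |
|---|---|---|---|
| 1% | 1% | 0.99% | 1.99% |
| 1% | 10% | 0.9% | 10.9% |
| 5% | 5% | 4.75% | 9.75% |
| 20% | 5% | 19.0% | 24.0% |
| 20% | 10% | 18.0% | 28.0% |
| 50% | 10% | 45.0% | 55.0% |

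In counts, for 1000 infants with p = 20% and m = 5%: 50 diaries are missing and 0.20 × 950 = 190 events are recorded. The row reads 190/1000 or 240/1000.

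The downward error is p·m and the upward error is m(1−p). The upward error is the larger whenever p is below 50%.

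**Step 4: rows over the study.** Take p = 20% and m = 5% per dose, with two doses and independence across doses.

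- True rate: 1 − 0.80² = 36.0%.
- Non-returner not counted: 1 − 0.81² = 34.4%, a relative loss of 4.5%.
- Non-returner in Any: 1 − (0.95 × 0.80)² = 42.2%.

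**Step 5: unequal return.** Suppose p = 20% in both groups, with non-return of 2% in one and 6% in the other.

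- Not counted: 0.20 × 0.98 = 19.6% against 0.20 × 0.94 = 18.8%, a spurious 0.8 points.
- In Any: 19.6% + 2% = 21.6% against 18.8% + 6% = 24.8%, a spurious 3.2 points in the opposite direction.

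**Step 6: a diary-based denominator.** Among infants or doses with diary data the expected rate is p: 20.0% in the 20%/5% case and 5.0% in the 5%/5% case.

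**The case against.** A reader of the general rule alone might infer that every solicited-event percentage is biased downwards by the non-return rate, so that the vaccine always looks better tolerated. The documents do not support that. The derivation rule in SAP 6.2.4.2 would push the Any rows upwards, and the contribution table disagrees with it, so the direction for those rows is undetermined. Nor is the loss m percentage points where it does occur. By dose it is a relative reduction of m, or p·m in points, which is 1 point at p = 20% and m = 5%.

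Two other inferences go too far. The 25% allowance in Protocol 9.2 concerns evaluability for the primary endpoint. The Per Protocol criteria do not include diary return, so that figure does not bound m. The idea that Dose 2 rows include infants who never received Dose 2 rests on silence: SAP 4.5 refers to events following administration, and SAP 6.1.5 counts a dose as a vaccination visit.

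The plan also has safeguards. Protocol 10.3.6 has cards checked with the parents at Visits 2 and 3 and unreturned cards pursued, which should keep m low. SAP 6.1.6 plans a compliance table by group and dose. As worded, however, that table counts returned sheets with at least one documented symptom, which is not a return rate.

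Finally, a diary-based denominator is not free of bias. If families with no event return fewer cards, it overstates p. That is a reason to keep a supportive table on the full Exposed Set. It does not justify leaving the three rules unreconciled.

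**Conclusion.** The point holds as a contradiction plus an unstated denominator. For an infant with no diary data, the plan says event-free in one place, counted in Any in another, and outside the Any numerator in a third. SAP 4.8 gives no order of precedence.

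On the Exposed Set base, grade-specific rows are understated by the factor (1−m) whichever rule is used. The Any row is uncertain by m percentage points. At p = 20% and m = 5% it misses the true rate by 1.0 point downwards or 4.0 points upwards; at p = 5% and m = 5%, by 0.25 points downwards or 4.75 upwards. These sizes rest on assumed p and m, on return being unrelated to events, and on the Exposed Set being the base. The actual error cannot be computed from the documents.

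The matter should be corrected, but it is of moderate weight. Safety is descriptive, whichever rule is chosen would apply to both groups, and the confirmatory immunogenicity objectives are untouched.

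**What to change.** Before unblinding, amend the SAP as follows.

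1. For solicited events, define the denominator as Exposed Set infants (or doses, for per-dose percentages) with documented diary data after that dose for by-dose rows, and after any dose for rows over the study.
2. Confine the event-free rule in Protocol 9.4.1.2 and SAP 4.1.2 to unsolicited events and concomitant medications, and record the departure from the protocol in SAP 4.8.
3. Amend the derivation rule in SAP 6.2.4.2 so that an infant with no occurrence status and no recorded event is not imputed into Any, and align it with the contribution table. Changing the denominator alone is not enough: an infant with one diary day but no yes/no status would still fall under the present imputation.
4. Keep the table on the full Exposed Set as supportive.
5. Reword SAP 6.1.6 so that it gives diary return by group and dose.

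The cost is SAP wording and one extra table. Reported grade-specific rates will be slightly higher.
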